An End of Treatment Phase (ETP) Visit will be performed 4 weeks after the final dose of the blinded study treatment is administered at Week 12. For participants who discontinue IP early, but have not withdrawn consent to participate in the study, an Early Withdrawal (EW) visit will be performed 4 weeks after the last dose of blinded study treatment. Participants should resume regular treatment for their asthma, as determined by the investigator, after protocol defined study assessments are completed. Three Follow-up visits will be performed 4, 8, and 12 weeks (Week 20, Week 24, and Week 28) after the ETP/EW Visit for safety assessments.

Following randomization participants will return to the clinic at least every 2 weeks for scheduled FP dose titration and assessment of asthma control until the last dose of blinded study treatment (Visit 9). Albuterol/salbutamol will be provided for symptomatic relief to be used on an as needed basis from Screening through to the ETP visit.

The maximum total duration of the study is approximately 33 weeks.

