4. OBJECTIVES AND ENDPOINTS

	Objectives	Endpoints
Pri	mary	
•	To evaluate the efficacy of GSK3772847, compared with placebo, administered intravenously every 4 weeks for 12 weeks (Week 0 – Week 12, 4 doses in total) in participants with moderately severe asthma.	Primary – Proportion of participants with loss of asthma control over Weeks 0-16 where 'loss of asthma control' is defined as at least one of the following: • Asthma Control Questionnaire (ACQ-5) score increase from baseline (measured at the end of Run-in) ≥0.5 point or • Pre-bronchodilator Forced expiratory volume in 1 second (FEV1) decrease from baseline (measured at the end of Run-in) >7.5 % or • Inability to titrate inhaled corticosteroid according to the pre-defined schedule (Section 5.1) or • A clinically significant asthma exacerbation (requiring oral corticosteroid [OCS] and/or hospitalisation).
Sec	condary	
•	To evaluate other aspects of efficacy of GSK3772847 compared with placebo in participants with moderately severe asthma.	 Other efficacy endpoints (at or by Week 16): Proportion of participants with a ≥0.5 point. ACQ-5 score increase from baseline. Proportion of participants who have prebronchodilator FEV1 decrease from baseline (measured at the end of Run-in) >7.5 %. Proportion of participants where inhaled corticosteroids (ICS) cannot be titrated in accordance with the pre-defined schedule. Proportion of participants who have a significant asthma exacerbation (requiring OCS and/or hospitalisation).

Objectives	Endpoints

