At Visit 4 (i.e. two weeks after Randomization) the open label background therapy will be switched from FP/Salmeterol 500/50 mcg BID to FP 500 mcg BID for 2 weeks. This will mark the beginning of the FP titration period. Every two weeks for the next six weeks the dose of FP will be reduced by approximately 50 % (i.e. FP 250 mcg BID at Visit 5 for 2 weeks, FP 100 mcg BID at Visit 6 for 2 weeks, then FP 50 mcg BID at Visit 7 for 2 weeks) until complete FP discontinuation at Visit 8, provided that the participant does not meet any of the loss of asthma control criteria. If any of the pre-defined criteria for loss of asthma control are met during the Treatment Period, participants will be withdrawn from the investigational product (IP) and should resume regular treatment for their asthma, as determined by the investigator.

Participants will be monitored for loss of asthma control through daily use of an eDiary and twice-daily PEF measurements. The participants will use the eDiary to record asthma symptoms, rescue medication use, and nocturnal awakenings due to asthma symptoms requiring rescue medication use. This information will be transmitted daily to a centralized server and available to the investigators. Alerts for pre-defined changes in PEF or asthma symptoms, indicative of worsening asthma, will be programmed into the eDiary with prompts to the participants to contact the investigator if any of the alert criteria are met (Section 9.1.2.3). Additionally, email notifications will be sent to the investigator, if any of the alert criteria are met, as soon as the data is transmitted to the centralized server. The investigator will make every effort to contact the participants in order to discuss the participants' symptoms and evaluate whether they experienced loss of asthma control.

For participants who receive all four doses of blinded study treatment, an End of Treatment Period (ETP) Visit will be performed 4 weeks after the final dose of the blinded study treatment is administered at Week 12. Participants should resume regular treatment for their asthma, as determined by the investigator, after protocol defined study assessments are completed. Three Follow-up visits will be performed 4, 8, and 12 weeks (Week 20, Week 24, and Week 28) after the ETP Visit for safety assessments.

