8.3. Lost to Follow Up

A participant will be considered lost to follow-up if he or she repeatedly fails to return for scheduled visits and is unable to be contacted by the study site.

The following actions must be taken if a participant fails to return to the clinic for a required study visit:

- The site must attempt to contact the participant and reschedule the missed visit as soon as possible and counsel the participant on the importance of maintaining the assigned visit schedule and ascertain whether or not the participant wishes to and/or should continue in the study.
- Before a participant is deemed lost to follow up, the investigator or designee must make every effort to regain contact with the participant (where possible, 3 telephone calls and, if necessary, a certified letter to the participant's last known mailing address or local equivalent methods). These contact attempts should be documented in the participant's medical record.
- Should the participant continue to be unreachable, he/she will be considered to have withdrawn from the study with a primary reason of lost to follow-up.

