10.2. Sample Size Determination

The study will randomize 74 participants per treatment arm with the aim of having 70 evaluable participants per arm. For the purpose of this study an evaluable participant is defined as a participant who completes the Week 16 clinic visit whilst remaining on IP or who withdraws from IP having met the primary endpoint. See Section 10.4.1 for how subjects who withdraw early from IP for reasons other than loss of asthma control are handled in the analysis.

In addition to testing the hypothesis in the overall population, the study will randomize a sufficient number of participants to evaluate trends in pre-defined subgroups (e.g. eosinophil strata).

The true proportion of participants that would experience a loss of asthma control on each treatment is unknown. However in a similar study of Dupilumab compared with placebo, the proportion of participants with loss of control were 6% and 44% for Dupilumab and placebo respectively. Table 4 gives the power to detect a statistically significant difference (at the two-sided 5% level) between the two treatments assuming the true proportion with loss of control on placebo is 44% and the true proportion with loss of control on active is 6%, 11%, 19% and 22% [Fleiss, 2003].

Table 4 Table of Power Achievable for Different Treatment Comparisons using N=70 per arm calculated using PASS

True proportion on Placebo	True proportion on GSK3772847	Reduction	Power
44%	6%	86%	> 99%
44%	11%	75%	> 99%
44%	19%	57%	90%
44%	22%	50%	80%

Assuming the true proportion with loss of control on placebo is 44%, then with 70 evaluable participants per arm, the study will have at least 80% power to detect a statistically significant difference between treatments assuming the true proportion with loss of control on GSK3772487 is at most 22% (Table 4).

With 70 evaluable participants per arm and assuming the true proportion with loss of control on placebo is 44%, the smallest observed difference that would lead to rejection of the null hypothesis (minimum detectable effect) is 31% corresponding to a proportion with loss of control on GSK3772847 of 28%.

There is a single primary endpoint so no adjustments are required for multiplicity.

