10.4. Statistical Analyses

10.4.1. Efficacy Analyses

All efficacy analyses will be performed on the mITT Population.

Endpoint	Statistical Analysis Methods
Primary	The primary endpoint proportion of subjects with loss of asthma control will be analyzed using both Bayesian and Frequentist methods. A subject is deemed to have met the endpoint of loss of asthma control if they meet the criteria for any of the components of the definition of loss of asthma control.
	The posterior probabilities that the ratio of the proportion of subjects with loss of asthma control on GSK3772847 compared with placebo is less than 1.0, 0.75, 0.5 and 0.2 (i.e. a 0%, 25%, 50% and 80% reduction) will be calculated analytically assuming a non-informative prior. This will be supported by an estimate of the ratio with a 95% credible interval. Results will also be presented for the two eosinophils strata separately.
	In addition, the proportion of participants with loss of asthma control will be analyzed using logistic regression allowing for baseline eosinophils strata. The odds ratio, 95% CI and p-value for the comparison of GSK3772847 with placebo will be presented.
	Results will also be presented for the two eosinophils strata separately by fitting a separate model with an additional term for eosinophil strata by treatment interaction. The effect of eosinophils as a continuous covariate will also be examined in a separate-logistic regression model.
	 Missing data will be handled using the following methods: 1) The loss of asthma control will be set to missing for participants who withdraw from IP prior to Week 16 for reasons other than loss of asthma control 2) A sensitivity analysis will be performed where participants who withdraw from IP prior to Week 16 for reasons other than loss of asthma control will have the endpoint set to loss of control
Secondary	The following secondary endpoints will be analyzed using the same statistical analysis as described for the primary endpoint: • Proportion of participants with a clinically significant asthma exacerbation

Endpoint	Statistical Analysis Methods
	 (requiring OCS and/or hospitalisation) Proportion of participants with Pre-bronchodilator FEV1 decrease from Baseline (measured at the end of Run-in) >7.5 % Proportion of participants with Inability to titrate inhaled corticosteroid

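### The primary missing-data rule depends on the recorded reason for stopping IP, so it can delete a loss of control that has already occurred, and it is unclear for participants lost after the last dose at Week 12

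*Protocol*

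**What the plan says.** The primary endpoint (Section 4) is the "Proportion of participants with loss of asthma control over Weeks 0-16", an ever/never composite. Section 10.4.1 derives it simply: "A subject is deemed to have met the endpoint of loss of asthma control if they meet the criteria for any of the components". The same section then gives two missing-data methods. In the primary analysis the outcome is "set to missing for participants who withdraw from IP prior to Week 16 for reasons other than loss of asthma control". In the sensitivity analysis those who withdraw from IP early for "reasons other than loss of asthma control will have the endpoint set to loss of control". The component endpoints use the primary rule. For time to loss of control, Section 10.4.1 censors only those early IP withdrawals who did not experience loss of control.

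Section 10.2 defines an evaluable participant as one who "completes the Week 16 clinic visit whilst remaining on IP or who withdraws from IP having met the primary endpoint", and refers to Section 10.4.1 for other early withdrawals.

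On timing, the end-of-treatment visit falls "4 weeks after the final dose of the blinded study treatment is administered at Week 12". Section 5.1 separates this path ("For participants who receive all four doses of blinded study treatment, an End of Treatment Period (ETP) Visit will be performed") from that of participants who stop IP early, who have an early withdrawal visit four weeks after their last dose. Under Section 8.3, of a participant who cannot be reached, "he/she will be considered to have withdrawn from the study with a primary reason of lost to follow-up". That is withdrawal from the study; IP is not mentioned.

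**The concern.** Whether an ever/never outcome is missing should depend on whether it was determined. Here it depends on one entry on the case report form. Section 8.1 requires a reason for discontinuing treatment and lists adverse event, lack of efficacy (including loss of asthma control), protocol deviation, investigator discretion and withdrawn consent. More than one can apply. ACQ-5 is completed weekly at home, so a rise of 0.5 can be on file before a participant withdraws consent. A QTc, liver or Holter stop can coincide with an FEV1 fall above 7.5%. If the other reason is the one recorded, an event that counts towards the primary endpoint leaves the primary analysis.

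A second problem has the same cause. The trigger names withdrawal from IP only, but dosing ends four weeks before the outcome window closes. Someone who received all four doses and was then lost may or may not count as a withdrawal from IP. Those weeks matter: FP has been stopped since Week 10, and a participant lost just after the Week 12 visit misses two of the three spirometry visits (Weeks 12, 14 and 16) that follow its complete withdrawal.

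**Working it through.** **1. The rules side by side.** Three participants, each classified by every rule:

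| Participant | Any-component rule (10.4.1) | Missing-data rule (10.4.1) | Evaluable (10.2) | Kaplan-Meier (10.4.1) |
|---|---|---|---|---|
| A. Threshold met, recorded reason is adverse event | loss of control | missing; loss in sensitivity | yes | event |
| B. Four doses, lost in Week 14, no component met | not met | not named; missing if this counts as IP withdrawal | no | censored if this counts as IP withdrawal |
| C. Taken off IP after dose four, seen at Week 16, no component met | not met | missing; loss in sensitivity | no | censored |

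A is a contradiction: three rules treat the outcome as determined and the fourth deletes it. The sensitivity analysis restores A, but only by also turning every event-free early stopper into a failure, so it does not isolate the problem. B is an ambiguity. C is consistent with Section 10.2, though it sets aside an outcome observed through Week 16.

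**2. The plan's own power figure.** Inputs from Section 10.2: n = 70 per arm, 44% v 22%, two-sided 5%. For the pooled z test,

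power = Φ{(p1 − p2 − 1.96·√[2p̄(1 − p̄)/n]) / √[(p1(1 − p1) + p2(1 − p2))/n]}.

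With p̄ = 0.33 this is (0.22 − 1.96 × 0.0795)/0.0773 = 0.83, and Φ(0.83) = 0.797. Table 4 states 80%, so it reproduces.

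**3. Size for A (illustration).** The documents give no count. Take 15/70 (21.4%) on active and 31/70 (44.3%) on placebo, ratio 15/31 = 0.484. Deleting determined events:
- one on active: 14/69 = 20.3%, ratio 0.203/0.443 = 0.458
- one on placebo: 30/69 = 43.5%, ratio 0.214/0.435 = 0.493
- one in each arm: ratio 14/30 = 0.467

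**4. Size for B (illustration).** Add participants lost after dose four to the same base. Four is the plan's whole non-evaluable allowance per arm (74 − 70). Setting them to missing leaves 0.484.

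| Lost (active/placebo) | Ratio if scored as controlled | Ratio if scored as loss |
|---|---|---|
| 4/4 | (15/74)/(31/74) = 0.484 | (19/74)/(35/74) = 0.543 |
| 4/0 | (15/74)/(31/70) = 0.458 | (19/74)/(31/70) = 0.580 |
| 0/4 | (15/70)/(31/74) = 0.512 | (15/70)/(35/74) = 0.453 |

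Scoring four per arm as controlled dilutes the design rates to 0.44 × 70/74 = 41.6% and 0.22 × 70/74 = 20.8%. Power at n = 74 is then 0.786 against 0.797.

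**The case against.** The best defence of the rule for participant A is that the case should be rare. Meeting a threshold is itself a mandatory IP stop (Section 8.1), and the investigator is expected to record which criterion was met (Section 9.1.5). Most such participants will therefore be coded as loss of control, and the analysis plan could settle precedence for the rest. The point about rarity stands. But the protocol does not leave this open: it states a rule, and the rule conflicts with three others.

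A reader might infer something stronger for Weeks 12-16: that participants lost there are scored as having kept control, in the sensitivity analysis as well. The documents do not support this. No section says so. The rule runs to Week 16, not Week 12. The Treatment Period is 16 weeks (Section 7.3). Section 10.2 speaks of remaining on IP to the Week 16 visit, and Section 8.1 lists withdrawn consent as a reason for stopping study treatment. The better reading is that these participants are missing in the primary analysis and failures in the sensitivity analysis. What remains is that the text does not say so, and Section 8.3 describes loss to follow-up as leaving the study.

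A reader might also infer that setting participant C aside is an error. It is a trade-off. Sections 5.1 and 8.1 have participants who stop IP resume regular asthma treatment, so later data may reflect restored therapy. Treating C as an error would also require that IP can be withdrawn after Week 12, the opposite of what the scored-as-controlled reading needs.

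**Conclusion.** The concern holds in this form: Section 10.4.1 classifies the primary outcome by the recorded reason for stopping IP, which can delete a determined loss of control and contradicts the any-component rule, Section 10.2 and the Kaplan-Meier rule. For Weeks 12-16 the wording is ambiguous but not demonstrably wrong.

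The size is unknown, because no document gives the number of discordant reasons or of late losses. Even if the whole planned allowance of four per arm were lost late and scored as controlled, balanced losses would leave the ratio unchanged and cost about one point of power. Only losses concentrated in one arm move the ratio, to 0.458 or 0.512, and that is a chosen extreme. A single deleted active-arm event also gives about 0.458. Section 10.1 judges success on posterior probabilities that the ratio lies below thresholds that include 0.5, so small shifts near that value are visible but unlikely to be decisive. The rule should be corrected before unblinding so that no primary outcome has to be classified afterwards.

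**What to change.** Reword Section 10.4.1 for the primary endpoint along these lines:

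- The outcome is loss of control if any component is met by Week 16 and at or before any IP stop, whatever reason for stopping is recorded.
- It is no loss of control only if the Week 16 visit is completed on IP with no component met.
- Otherwise it is missing in the primary analysis and loss of control in the sensitivity analysis. This expressly includes study withdrawal or loss to follow-up after the fourth dose.

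Give the component endpoints the same precedence: a component that was met counts, whatever reason is recorded. A participant who stopped because a different component was met should keep the present handling and not become missing.

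Add a supplementary analysis that uses outcomes observed to Week 16 for participants taken off IP after the fourth dose. It should be supplementary because regular asthma treatment may have resumed.

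The cost is a few sentences in the protocol and the analysis plan, and a few participants classified differently. No visit, assessment or stopping criterion changes.

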For participants who discontinue IP early, but have not withdrawn consent to participate in the study, an early withdrawal (EW) visit will be performed 4 weeks after the last dose of blinded study treatment. These participants should continue in the study and complete all assessments at the remaining protocol-defined visits until their EW visit. Participants should resume regular treatment for their asthma, as determined by the investigator. Three Follow-up visits will then be performed 4, 8, and 12 weeks after the EW visit for safety assessments.

Participants who discontinue IP early and withdraw consent to participate in the study should complete as many assessments planned for the EW visit as possible.

Following randomization participants will return to the clinic at least every 2 weeks for scheduled FP dose titration and assessment of asthma control until the last dose of blinded study treatment (Visit 9).

Albuterol/salbutamol will be provided for symptomatic relief to be used on an as needed basis from Screening through to the ETP visit.

The maximum total duration of the study is approximately 33 weeks.

An independent Safety Review Committee (iSRC) will periodically review unblinded safety data to protect and maintain participant safety whilst maintaining scientific validity. Members of the iSRC will be independent of the project. The data will include, but not necessarily be limited to SAEs, Holters, and ECGs. Details are described in the iSRC Charter.

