9.2. Adverse Events

The definitions of an AE or SAE can be found in Appendix 4.

Asthma exacerbations or worsening of asthma should not be recorded as an AE, unless they meet the definition of an SAE. For the purposes of this study, asthma exacerbations

will be collected and recorded on the exacerbations log in the eCRF. The treatment details must also be recorded in the eCRF. The time period for collection of asthma exacerbations will begin from screening and will end after the follow-up period has been completed.

The investigator and any designees are responsible for detecting, documenting, and reporting events that meet the definition of an AE or SAE and remain responsible for following up AEs that are serious, considered related to the study treatment or the study, or that caused the participant to discontinue the study treatment (see Section 8).

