	 according to the pre-defined schedule (Section 5.1) Proportion of participants with ACQ-5 score increase from Baseline (measured at the end of Run-in) ≥0.5 point. Proportion of participants with a clinically significant asthma exacerbation or inability to titrate ICS according to the pre-defined schedule. In these analyses, the endpoint will be set to missing for participants who withdraw from IP prior to Week 16 for reasons other than loss of asthma control.
	Time to loss of asthma control will be analyzed using Kaplan-Meier analysis. Percentiles for time to loss of control will be presented for both treatment groups, along with graphical survival plots. Any early withdrawals from IP that did not experience loss of control will be censored. Results will be presented for both of the two eosinophil strata separately, and combined.
	The following endpoints will be analyzed using repeated logistic regression. This analysis will be repeated including an additional term for eosinophil strata by treatment by visit interaction to provide estimates for the two eosinophil strata separately:
	 Proportion of ACQ-5 responders (a ≥0.5 point improvement from baseline at Week 16) Proportion of SGRQ responders (at least a 4 unit improvement from
	baseline at Week 16 These analyzes will be performed using two different methods for handling missing data:
	If endpoint at a visit is missing then the responder status is set to missing
	2) If endpoint at a visit is missing and the endpoint is also missing at all subsequent visits then the responder status is set to non-responder. The odds ratio, 95% CI and p-value for the comparison of GSK3772847 with placebo will be presented for all models.
	Mixed model repeated measures will be used to analyze the following endpoints. The baseline value of each endpoint will be included along with baseline*visit and treatment*visit interactions. Treatment differences, 95% confidence intervals and p-values will be presented.
	 Change from baseline in ACQ-5 absolute score Change from baseline in SGRQ total score Change from baseline in Pre-bronchodilator FEV1
	Change from baseline in FeNO This analysis will be repeated including an additional term for eosinophil

Endpoint	Statistical Analysis Methods
	strata by treatment by visit interaction to provide estimates for each eosinophil strata separately. No adjustment will be made for missing data.

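### After loss of control, the responder rules can hide a benefit by dropping or miscoding participants, and the component tests depend on how early the other criteria were met

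*Protocol*

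**What the plan says.** Under Protocol Section 5.1, when any loss-of-control criterion is met, "participants will be withdrawn from the investigational product (IP) and should resume regular treatment for their asthma". These participants then "complete all assessments at the remaining protocol-defined visits until their EW visit", which falls four weeks after the last dose. The three later visits are for safety, and the Schedule of Activities shows no spirometry, ACQ-5 or SGRQ at them.

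Section 10.4.1 then fixes two sets of rules.

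- **ACQ-5 and SGRQ responders** (repeated logistic regression). Method 1: "If endpoint at a visit is missing then the responder status is set to missing". Method 2: a value missing at a visit and at all subsequent visits becomes non-response. Neither is named as the main analysis.
- **Five component proportions**, analysed as the primary endpoint is, with posterior probabilities, odds ratio and p-value. "In these analyses, the endpoint will be set to missing for participants who withdraw from IP prior to Week 16 for reasons other than" losing control. Participants withdrawn because of loss of control therefore stay in the denominator of every component.

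Section 9.2 says of exacerbations: "The time period for collection of asthma exacerbations will begin from screening and will end after the follow-up period has been completed".

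**The concern.** Losing control is the outcome the drug is meant to prevent, and it is also the event that ends efficacy measurement. An analysis restricted to participants with a Week 16 value is therefore largely restricted to those who kept control, and the two arms are selected differently. A drug that keeps more people in control retains people who may be harder to bring to response, while placebo failures leave the comparison.

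Method 2 repairs this only where nothing is recorded afterwards. A value measured after loss of control, on resumed regular treatment and up to the early withdrawal (EW) visit, is taken at face value. For a loss after the Week 12 dose, EW falls at Week 16 itself, so recovery on resumed treatment can be scored as a Week 16 response.

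For FEV1 and ACQ-5, meeting one criterion shortens the time in which another can be observed. The arm with more early failures has less opportunity to show each remaining component, so a stand-alone test of one component mixes its own effect with the timing of the others.

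**Working it through.** **Inputs.** Section 10.2 gives loss of control of 44% on placebo and 22% on active as one planning case (6% is the most favourable), and 70 evaluable per arm. The protocol gives no responder rates and no split of losses by component, so those below are assumptions.

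**The plan's own figure.** Two-sided 5% test of two proportions, pooled variance, n = 70: z = [0.22·√70 − 1.96·√(2·0.33·0.67)] / √(0.44·0.56 + 0.22·0.78) = (1.841 − 1.303)/0.647 = 0.83, power 79.7%. Table 4 states 80%, so it reproduces.

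**Responders at Week 16** (odds ratio above 1 favours active). Take first the case where no participant who lost control has a Week 16 value.

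1. Assume 50% respond among those still controlled, in both arms.
   - Method 1: 50% vs 50%, OR 1.00.
   - Loss of control as non-response: active 0.78 × 0.50 = 39%, placebo 0.56 × 0.50 = 28%. OR = (0.39/0.61)/(0.28/0.72) = 1.64.
2. Assume instead that participants kept in control only by the drug (44% − 22% = 22% of the arm) respond at 25%.
   - Active responders: 0.56 × 0.50 + 0.22 × 0.25 = 33.5%.
   - Method 1: 0.335/0.78 = 42.9% vs 50%, OR 0.75.
   - Loss as non-response: 33.5% vs 28%, OR 1.30. The direction reverses.
3. Vary the assumptions: 40–60% response in those still controlled, 10% up to the same rate in those kept in control only by the drug, active loss 6% or 22%. Method 1 gives ORs of 0.44–1.00; loss as non-response gives 1.10–2.56.

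**Losses after the Week 12 dose** keep a Week 16 value. If these are 10%, 30% or 50% of losses and all are non-responders, the method 1 OR of 0.75 in case 2 becomes 0.83, 0.96 or 1.08, against 1.30. In case 1 with 30%: active 0.39/(0.78 + 0.066) = 46.1%, placebo 0.28/(0.56 + 0.132) = 40.5%, OR 1.26 against 1.64.

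Now assume half of that 30% score as responders on resumed treatment, and apply method 2 to case 1. Active is 0.39 + 0.22 × 0.3 × 0.5 = 42.3%; placebo is 0.28 + 0.44 × 0.3 × 0.5 = 34.6%. OR = (0.423/0.577)/(0.346/0.654) = 1.39 instead of 1.64.

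**Components** (ratio below 1 favours active). Assume constant hazards and no capture of a component after another has been met. The crude proportion for component k is h_k/H × (1 − e^(−H)), with H the total hazard. On placebo, H = −ln(0.56) = 0.58.

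- Uniform effect, hazard ratio 0.43 on everything (total 44% vs 22%): crude ratio 0.50 against a net ratio of 0.44 (component is 20% of the hazard) or 0.47 (50%).
- Component is 20% of the placebo hazard, hazard ratio 0.9 on it and 0.25 on the rest: 8.8% vs 9.4%, crude ratio 1.06 against net 0.91.
- FEV1 hazard 0.18 with no drug effect, other criteria 0.40 cut by 75%: placebo 0.18/0.58 × (1 − e^(−0.58)) = 13.7%; active 0.18/0.28 × (1 − e^(−0.28)) = 15.7%. Ratio 1.15 where the truth is 1.

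**Exacerbation follow-up.** In the earliest case the last dose is at Week 0, EW at Week 4 and follow-up visits at Weeks 8, 12 and 16. Every retained participant is thus followed to at least Week 16.

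**The case against.** Several points on the other side are sound.

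- Method 2 is prespecified. Where no Week 16 value exists after loss of control, it gives exactly the 39% vs 28% result. What remains is that it accepts values recorded on resumed treatment and is not designated as the main method.
- Method 1 does not erase participants. A repeated model keeps their visits up to EW, and losses after the Week 12 dose keep Week 16. As shown, this softens the bias.
- A reader might infer that the component rule codes every unmet criterion as event-free. The text does not say so. Exacerbations are logged to the end of follow-up, loss of control during the taper could be coded as inability to titrate, and Section 9.1.5 lets the investigator record more than one criterion. Such coding may properly sit in the analysis plan.
- A reader might infer that EW values will be assigned to Week 16 because the Schedule of Activities puts ETP and EW in one Week 16 column. No analysis rule states this.
- Crude proportions between randomised arms are a legitimate total-effect comparison. Replacing them with cumulative incidence of the first criterion met would not help: under the model above it is the same quantity and returns the same 13.7% vs 15.7%.

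What these points leave standing is the responder defect and the stand-alone testing of components whose observation is cut short by other components.

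**Conclusion.** The concern holds for the responder analyses. At the protocol's 44% vs 22%, method 1 can remove a benefit (OR 1.00 vs 1.64) or reverse it (0.75 vs 1.30). The size depends on assumed response rates and on how many losses follow the Week 12 dose. Method 2 is much better but still allows recovery on resumed treatment to count as response.

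For the component proportions the effect is smaller and conditional. A drug acting equally on all criteria is mildly attenuated (0.50 against 0.44–0.47). A spurious ratio above 1 needs effects that differ between components, so the stronger reading that the component results would generally turn benefit into harm is not supported.

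Severity is moderate. These are secondary endpoints in a proof-of-concept study whose hypothesis and success assessment rest on the primary ratio, and the primary composite counts every loss of control as an event whichever criterion is met.

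**What to change.** 1. Make the main ACQ-5 and SGRQ responder analysis one in which status is non-responder at every visit after loss of control, whatever value is recorded. Keep method 1 as a sensitivity analysis.
2. State that EW values obtained before Week 16 are not assigned to Week 16.
3. Analyse logged exacerbations to Week 16 for all retained participants, regardless of IP status.
4. Report FEV1, ACQ-5 and titration failure descriptively, as the criterion or criteria met at loss of control, and drop their stand-alone posterior probabilities, odds ratios and p-values.

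The cost is analysis wording and programming, using data already collected. It should be settled before unblinding, because the choice of responder method can change the direction of the result.
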